Study Protocol and Statistical Analysis Plan

Title:

**The Effect of Music Therapy on Cognition in
Neurorehabilitation – A
Feasibility Randomized Controlled Trial**

Date:

8 April. 25

Expected Risks and Benefits

The investigators do not foresee any additional risks to subjects who participate in the study, compared to the day-to-day standard therapy protocol, as the interventions will be implemented in the same physical environments, with the same equipment and personnel. There could also be a potential risk of breach of confidentiality and anonymity. See Safety Measurement on how the investigators aim to minimize the risk and protect the confidentiality of subjects. On the other hand, potential benefits may include but are not limited to, improved cognitive functions after the music therapy interventions.

Safety Measurements

In the event of any adverse event, the standard protocol will be implemented. Subjects' confidentiality will be guarded by assigning IDs, which link to their names in a separate password-protected document accessible via a password-protected user account in a laptop or desktop, only accessed by the investigator. All physical documents will be locked in a designated file cabinet in a locked office where only the investigator has the key. All documents will be kept for two years before they are shredded. All subjects may raise any concerns about the research to the music therapist directly, or the music therapist's supervisor at the facility. A phone number and an email address will be given to all subjects in the consent form. They may also report to the person in charge of the ethics committee team, whose contact information will be provided on the consent form as well.

Data Collection and Analysis

Data will be analyzed using descriptive and inferential statistics. As this is a feasibility/exploratory study, the number of subjects is set at a minimum of 30, given the capacity of the music therapist. It is intended for the data collection phase to not exceed 1 year. After data collection is complete for a minimum of 30 subjects, data analysis will begin. The pre-and post-intervention scores, across each condition, for each subject, as well as for subjects undergoing the same condition, will be compared, to show the effect size, with 95% Confidence Interval.

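### Does a minimum of 30 subjects with no stated ceiling let the sample grow after results are seen, and so undermine the 95% interval?

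*Combined protocol and SAP*

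**What the plan says.** Everything relevant is in the Data Collection and Analysis section of the combined protocol and SAP.

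- **Size:** "As this is a feasibility/exploratory study, the number of subjects is set at a minimum of 30". The reason offered is what one music therapist can handle: "the number of subjects is set at a minimum of 30, given the capacity of the music therapist". There is no power or precision calculation.
- **Duration:** "It is intended for the data collection phase to not exceed 1 year".
- **Trigger for analysis:** "After data collection is complete for a minimum of 30 subjects, data analysis will begin".
- **Analysis:** "Data will be analyzed using descriptive and inferential statistics". Pre- and post-intervention scores are compared "to show the effect size, with 95% Confidence Interval".

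The section states no maximum, no closing date, no interim analysis, no significance level and no criterion for success. It does not say that subjects will be added once results are known.

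**The concern.** Three features of the wording, taken together, look like an open-ended design. Thirty is a floor. Analysis is triggered when that floor is complete, not when enrolment is closed. The year is an intention, not a limit. The capacity argument adds to the unease, because limited capacity would usually explain a ceiling, yet here it supports a minimum.

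Read strictly, this allows an investigator to compare scores at 30, find the result inconclusive, recruit more and compare again. An unadjusted 95% interval reported at whichever look turned out favourable would exclude zero too often when there is no effect. The exploratory label does not remove that problem. The plan commits to inferential statistics and to intervals, and an effect size from this trial could inform the design of a later one. It is also unclear whether the 30 are randomised subjects or subjects with both scores.

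**Working it through.** **Inputs from the plan:** at least 30 subjects; data collection intended to last up to 1 year; effect sizes with 95% intervals. **Assumptions not in the plan:** two equal arms, normally distributed change scores, two-sided 5% at each look, and every look schedule below.

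**1. The plan's own figure.** Thirty cannot be reproduced by calculation, because it rests on capacity and the section gives no effect size, SD or power. For scale only, with 15 per arm the between-arm half-width is t(0.975, 28) × √(1/15 + 1/15) = 2.048 × 0.365 = 0.75 SD.

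**2. Reading the sentences in order.** The section gives the number of subjects, then the length of a collection phase, then says that analysis comes after collection is complete. That describes two consecutive phases and one analysis. The words setting a minimum then mean that analysis does not start below 30. To obtain a repeated-look design, a reader must add a second enrolment period and a second analysis, and the section mentions neither.

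**3. Error under the ordinary reading.** With one analysis at N = 30, 200,000 simulated null trials gave an interval excluding zero in 5.03% between arms and 4.97% within an arm of 15. Both are nominal.

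**4. Error if the looks were used opportunistically.** Under no effect, the z-statistics at sizes N1 < N2 have correlation √(N1/N2). For 30 and 40 this is √0.75 = 0.866, and the chance that at least one look excludes zero is 1 − P(|Z1| < 1.96 and |Z2| < 1.96) = 0.074. Results by schedule (simulated t intervals, 200,000 null trials each):

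| Looks (total N) | Between arms | Within one arm (half the N) |
|---|---|---|
| 30 | 5.0% | 5.0% |
| 30, 40 | 7.4% | 7.6% |
| 30, 34, 38, 42 | 9.0% | 9.0% |
| 30, 40, 50, 60 | 10.5–10.7% | 10.7–11.0% |

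The ranges show the spread between repeat simulations. The normal approximation gives 10.6% between arms for the last row. These are rates for stopping at the first interval that excludes zero or, equivalently, for counting any such look. A milder rule, extending from 30 to 40 only when the first p-value lies between 0.05 and 0.20, gives about 7.0%.

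**5. Error if extension does not depend on the results.** If the trial always continues and reports only the last interval, that interval is an ordinary fixed-size interval at the larger N. In simulation it excluded zero in 5.0% of null trials for each of the three multi-look schedules. When extension from 30 to 40 was decided independently of the data, the figure was 4.9%.

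Comparing steps 4 and 5 shows that enlarging the sample after a comparison does not by itself damage the interval. The damage comes from letting the observed scores decide whether to continue or which interval to report.

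**The case for a change.** The best case for a change is that a combined protocol and SAP exists to settle such matters in advance. The trigger is tied to completing a minimum, not to closing enrolment, so the text does not enforce the reading in step 2. One sentence would do so, and no feature of an exploratory study makes result-driven stopping harmless to an interval. The factual part of this stands: there is no stated maximum, and a clarifying sentence would do no harm.

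It does not amount to an error in the plan. The claim that coverage fails whenever the sample is extended after a comparison is wrong, as step 5 shows. The figures of 7% to 11% belong to rules the plan does not contain, applied at sizes it does not mention. Therapist capacity and the intended year, though not firm, are practical brakes on extension.

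A hard closing rule is not free either. Closing at a fixed number or a fixed date, whichever comes first, could end a slow trial below the stated floor of 30. Fixing 30 randomised subjects has its own price: with an assumed 20% dropout, 24 subjects would have both scores, and the half-width would rise from 0.75 to 0.85 SD (0.847/0.748 = 1.13, so 13% wider). Keeping 30 complete would need 30/0.8 = 37.5, so 38 randomised, which has to fit the same capacity.

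Whether 30 counts randomised or completed subjects, and how missing post-intervention scores are handled, are fair questions. They are separate from adding subjects after results. They concern unstated policies, not a rule that the plan states wrongly.

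**Conclusion.** No change to the plan is needed. The absence of a ceiling is a gap in detail. Its natural completion is one collection phase with at least 30 subjects followed by one comparison, which keeps the error at the nominal 5%.

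Were the gap exploited, the chance of a false exclusion of zero would rise to about 7% with one result-driven extension from 30 to 40, and to about 10.5% with stopping at the first significant look among 30, 40, 50 and 60. Those figures assume two equal arms and look schedules that the documents do not give. In a feasibility study with no stated significance level or success criterion, they describe a hypothetical misuse and not the planned analysis.

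The conclusion rests on scores being compared once, after collection has ended. A report that gives the final number of subjects and when enrolment stopped would let a reader confirm this.

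### The plan attaches an effect size and 95% CI to each subject as well as to each group, but describes nothing from which a single subject's treatment effect could be estimated

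*Combined protocol and SAP*

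**What the plan says.** The title calls the study a "Feasibility Randomized Controlled Trial". The planned comparison is a single sentence under Data Collection and Analysis: "The pre-and post-intervention scores, across each condition, for each subject, as well as for subjects undergoing the same condition, will be compared", and the purpose is "to show the effect size, with 95% Confidence Interval". The only other statement on method is general: "Data will be analyzed using descriptive and inferential statistics".

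The phrase "across each condition, for each subject, as well as for subjects undergoing the same condition" sets two levels of comparison, the individual subject and the group sharing a condition. The closing clause on effect size and interval follows both and is not limited to either.

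The plan does not state:
- whether the design is parallel or crossover, or what the conditions are;
- how many conditions or pre/post assessments each subject has;
- which type of effect size is meant;
- where a within-subject variance would come from;
- how period, order, practice or carry-over would be handled.

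**The concern.** A treatment effect for one person needs two things: a comparison with what would have happened to that person under another condition, and a measure of how much the score varies within that person. The plan provides neither. A statistician following the sentence literally would have to report, subject by subject, an effect size and interval that either cannot be formed from that subject's data or does not isolate the effect of therapy.

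The section on expected risks and benefits names "improved cognitive functions after the music therapy interventions" as a possible benefit. A per-subject effect with an interval could easily be read as evidence of that benefit in an individual, when test noise, recovery over time, practice on the test or the order of conditions could produce the same result.

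**Working it through.** **Inputs.** The only figure in the plan is the sample size: "the number of subjects is set at a minimum of 30, given the capacity of the music therapist". It rests on capacity and has no statistical inputs, so there is nothing to reproduce, and this point does not affect it. The reliability, drift and carry-over values below are assumptions.

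**1. One pre/post pair, subject's own data only.** With k pairs, the 95% half-width for a subject's mean change is t(0.975, k−1) × SD_w / √k, where SD_w is that subject's SD of change.
- k = 1: 0 degrees of freedom, so no interval.
- k = 2: 12.706 / √2 = 8.98 SD_w.
- k = 3: 4.303 / √3 = 2.48 SD_w.
- k = 4: 3.182 / √4 = 1.59 SD_w.

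Repeated pairs therefore give an interval, but a very wide one when pairs are few, and it is an interval for change.

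**2. One pair, borrowed measurement error.** In units of the between-subject SD, with test-retest reliability r, the half-width for one change is 1.96 × √(2(1−r)). For the difference between two independent changes it is 1.96 × √(4(1−r)).

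| Assumed r | One change | Difference of two changes |
|---|---|---|
| 0.7 | 1.96 × 0.775 = 1.52 | 1.96 × 1.095 = 2.15 |
| 0.8 | 1.96 × 0.632 = 1.24 | 1.96 × 0.894 = 1.75 |
| 0.9 | 1.96 × 0.447 = 0.88 | 1.96 × 0.632 = 1.24 |

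With one condition per subject, only the middle column applies. It describes how far the score moved, with no second condition to set against it.

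**3. Two conditions per subject, one period each.** Let t be the effect of music therapy, p1 and p2 the gains that occur in each period anyway, and w the fraction of the effect that fades during a following control period. The contrast is music change minus control change.
- Music first: (t + p1) − (p2 − wt) = t + (p1 − p2) + wt.
- Control first: (t + p2) − p1 = t − (p1 − p2).

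For an individual, the period difference enters in full, with its sign set by order. If t = 0 and p1 − p2 = 0.3 SD (assumed), a music-first subject shows +0.3 SD and a control-first subject −0.3 SD, with no treatment effect at all.

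**4. The same model at group level.** The average over balanced orders is t(1 + w/2). The common period effect cancels: in the example, 15 subjects at +0.3 and 15 at −0.3 average 0. Differential carry-over does not cancel. It biases the average only if both t and w are non-zero. Full fading (w = 1) gives 1.5t; benefit that keeps building (w below 0) shrinks the estimate.

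**5. What the group level can support.** In SDs of change, the half-width for mean change within one condition is 2.145 / √15 = 0.55 at n = 15 and 2.045 / √30 = 0.37 at n = 30. For a difference between two parallel arms of 15 (an assumed 1:1 split) it is 2.048 × √(2/15) = 0.75. These are wide, but they are properly defined.

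**The case against.** The strongest defence is that the sentence may mean something ordinary: take each subject's paired change, summarise it by condition, and give the effect size and interval for the group. The wording allows that, and on that reading no per-subject interval is promised. It is not what the grammar says, however, and a plan should not leave the level of inference to interpretation. If this was the intention, the fix costs the investigators nothing.

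Several stronger conclusions that a reader might draw are not supported:
- *No interval can exist for a single subject.* This is too absolute. Repeated pairs or a borrowed measurement error would give one for change, and the number of assessments is not stated. A replicated single-case design with randomised order could even support a subject-level effect, but the plan describes no such design.
- *A pooled within-subject effect must be biased even with balanced order.* Step 4 shows that this needs non-zero carry-over and a non-zero effect, and the direction is not fixed.
- *The trial will name individual responders.* The plan nowhere says so and describes itself as exploratory. This is a risk, not a stated intention.
- *The study is a crossover, or is parallel.* The documents settle neither.

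**Conclusion.** The point holds in a limited form. As written, the sentence promises an effect size with a 95% CI at the level of the individual, and the plan supplies no replication, variance source or period term to support it. This is a stated output that would be unsound if produced, not only a missing detail.

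Its size depends on facts the plan omits. With one pair per subject, the subject's own data give no interval, and the borrowed-error interval of ±0.88 to ±1.52 SD (reliability 0.9 to 0.7, assumed) is for change only. With several unreplicated conditions, the individual contrast is displaced by the whole period difference, with any carry-over added, and measurement noise alone is ±1.24 to ±2.15 SD. At group level, balanced randomised order would remove a common period effect but not differential carry-over, if there is any.

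Wrong as written, low severity: the study is an exploratory feasibility trial and rewording cures the fault.

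**What to change.** Replace the comparison sentence with:

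> Individual pre and post scores will be listed and plotted descriptively; no effect size, confidence interval or attribution to music therapy will be given for a single subject. Effect sizes with 95% CI will be estimated at group level, as the difference in pre-to-post change between the randomised conditions.

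If subjects receive more than one condition, add:

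> The group-level model will include subject, period and condition, and possible carry-over will be stated as a limitation.

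State alongside this how many conditions and assessments each subject has. Naming the contrast between randomised conditions matters: a group-level pre/post change within one condition would still mix therapy with recovery and practice.

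There is no need to restrict the analysis to each subject's first condition. In a crossover that would trade precision for protection against carry-over, and this point does not require it.

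The cost is a few sentences of wording, with no added subjects, visits or staff. What is given up is the inferential claim for single subjects; their data are still shown.

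### The plan names no between-condition estimator and no baseline adjustment; if the arms are parallel, using the pre-intervention score as a covariate would usually sharpen the effect estimate and protect it from chance imbalance

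*Combined protocol and SAP*

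**What the plan says.** The title calls the study a "Feasibility Randomized Controlled Trial". All of the analysis text is in the section Data Collection and Analysis.

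- On method: "Data will be analyzed using descriptive and inferential statistics". No test, model or covariate is named.
- On the comparison: "The pre-and post-intervention scores, across each condition, for each subject, as well as for subjects undergoing the same condition, will be compared". Its stated purpose is "to show the effect size, with 95% Confidence Interval". The type of effect size is not defined.
- On size: "the number of subjects is set at a minimum of 30, given the capacity of the music therapist".

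The document does not give the number of arms, the allocation ratio, whether the design is parallel or crossover, the cognitive instrument, or the correlation between pre and post scores.

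**The concern.** A pre-intervention score is to be collected, but its only stated use is comparison with the post score, subject by subject and within condition. A randomised trial estimates its effect by contrasting the randomised conditions, and the plan does not say how that contrast will be formed.

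Two simple choices are available to an analyst who follows the text. A contrast of changes (post minus pre) fixes the coefficient on the pre score at 1. A contrast of post scores fixes it at 0. Estimating the coefficient is usually more efficient than either, and it corrects for whatever baseline difference chance has produced.

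The stake is the one quantity the plan promises, an effect size with its interval. The sample is set by therapist capacity, so extra precision cannot readily come from recruiting more subjects. If the choice stays open until the baseline table has been seen, the estimate can also depend on which contrast is picked.

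**Working it through.** The plan has no power or precision figure to reproduce; 30 is a capacity figure.

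**Inputs**
- From the document: at least 30 subjects; a 95% interval; a pre and a post score.
- Assumed: two parallel arms of n = 15 (N = 30); equal pre and post SD, set to 1 so that results are in SD units; pre-post correlation r, shown over a range.

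**Standard error of the between-arm difference**
- Post score: √(2/n) = √(2/15) = 0.365
- Change score: 0.365 × √[2(1 − r)]
- ANCOVA: 0.365 × √(1 − r²) × √[1 + 1/(N − 4)]. The last factor, √(27/26), is the small-sample cost of estimating the slope.

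The 95% half-width multiplies these by the t quantile: 2.048 on 28 df for the first two and 2.052 on 27 df for ANCOVA.

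*Example, r = 0.5.* Change: 0.365 × √1 × 2.048 = 0.748. ANCOVA: 0.365 × √0.75 × √(27/26) × 2.052 = 0.661. The ratio is 0.661/0.748 = 0.884, so ANCOVA is 12% narrower.

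| r | Change | Post | ANCOVA | ANCOVA vs change | ANCOVA vs post |
|---|---|---|---|---|---|
| 0.2 | 0.946 | 0.748 | 0.748 | 21% narrower | no gain |
| 0.3 | 0.885 | 0.748 | 0.728 | 18% narrower | 3% narrower |
| 0.5 | 0.748 | 0.748 | 0.661 | 12% narrower | 12% narrower |
| 0.6 | 0.669 | 0.748 | 0.611 | 9% narrower | 18% narrower |
| 0.7 | 0.579 | 0.748 | 0.545 | 6% narrower | 27% narrower |
| 0.8 | 0.473 | 0.748 | 0.458 | 3% narrower | 39% narrower |
| 0.9 | 0.335 | 0.748 | 0.333 | under 1% narrower | 56% narrower |
| 0.95 | 0.237 | 0.748 | 0.238 | no gain | 68% narrower |

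The squared ratio of half-widths, change to ANCOVA, is 1.28, 1.20, 1.13 and 1.07 at r = 0.5, 0.6, 0.7 and 0.8. Multiplied by 30, these correspond to about 38, 36, 34 and 32 subjects analysed by change scores.

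**Chance imbalance**
- The baseline difference D between arms has SD 0.365. Since 0.5/0.365 = 1.37, P(|D| > 0.5 SD) = 2 × 0.0855 = 17%.
- Given D, the change-score estimate shifts by −(1 − r)D and the post-score estimate by +rD. The ANCOVA shift is zero on average. The post-score estimate minus the change-score estimate is exactly D.
- When one arm starts more than 0.5 SD higher, the mean of D is 0.365 × φ(1.37)/0.0855 = 0.667, where φ is the standard normal density. The average shift is then −0.5 × 0.667 = −0.33 (r = 0.5) to −0.2 × 0.667 = −0.13 (r = 0.8) for change scores. For post scores it is +0.33 to +0.53.

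**Simulation check.** With 20,000 trials at each of r = 0.3, 0.5, 0.7 and 0.9 and no true effect, all three estimators averaged within 0.006 of zero. Their empirical SDs agreed with the formulas to within 0.003.

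**The case against.** The strongest reply is that the plan is silent rather than wrong. A reader might infer that it has chosen an unadjusted change-from-baseline analysis. The text does not support that: it names no model, does not exclude adjustment, and its reference to inferential methods could cover ANCOVA. What stands is that nothing has been prespecified, and that the pre score has no role beyond being compared with the post score.

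A reader might also infer that an unadjusted effect would be biased. It would not be: randomisation makes each of these estimators unbiased on average. The shifts above hold only given an observed imbalance. They still matter to the reader of a single trial with a single baseline table.

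Third, the gain depends on a correlation that the documents do not give. At 0.8 the gain over change scores is worth about two subjects, and by 0.9 it is negligible. At 0.2 or below there is none over post scores. This objection stands and limits the size of the point. But the correlation is unknown in advance, and ANCOVA is at or near the best of the three across the range.

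Fourth, the wording about conditions for each subject could describe a crossover, while the phrase about subjects undergoing the same condition fits parallel arms. In a crossover the figures above would not apply directly. Finally, this is an exploratory study with at least 30 subjects, and no stated decision hangs on the interval.

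**Conclusion.** The point holds in limited form. The plan names neither a between-condition estimator nor a baseline adjustment, and its only stated use of the pre score is a pre-post comparison. For a parallel design with 15 per arm and equal SDs, ANCOVA would narrow the interval by 12% down to 3% relative to change scores for correlations from 0.5 to 0.8. It would also remove the opposing shifts that follow a chance imbalance. The two-arm parallel design, the arm size and the correlation are assumptions.

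The documents do not support saying that the plan commits to an unadjusted analysis, that its estimate will be biased, or that a loss of precision is certain. The consequence is a less precise and less stable exploratory estimate, not a failed confirmatory test. The change is worth making because it uses data already planned and settles the estimator before the baseline table is seen.

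**What to change.** In Data Collection and Analysis, replace the comparison sentence with wording such as:

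> The effect of music therapy is estimated from a linear model of the post-intervention score on randomised condition, with the pre-intervention score as covariate. The adjusted difference between conditions, in score points, is reported with its t-based 95% confidence interval. Pre-post comparisons within condition are descriptive.

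State whether the design is parallel or crossover. If subjects receive more than one condition, use the same baseline adjustment in a model with subject and period terms.

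The cost is a few sentences of SAP text and one degree of freedom, with no new data. At N = 30 that degree of freedom and the slope estimation outweigh the gain over change scores only if the correlation exceeds about 0.9. Against post scores they do so only if it is below about 0.2.

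### Does the plan analyse subjects by the treatment they received, and only those who complete, instead of by randomised arm?

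*Combined protocol and SAP*

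**What the plan says.** The title of the combined protocol and SAP calls the study a "Feasibility Randomized Controlled Trial". The analysis plan is one paragraph, under Data Collection and Analysis. It bears on this point in four places:

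- **Type of analysis:** "Data will be analyzed using descriptive and inferential statistics".
- **Size:** "the number of subjects is set at a minimum of 30, given the capacity of the music therapist". The number comes from capacity, not from a power calculation.
- **Timing:** "After data collection is complete for a minimum of 30 subjects, data analysis will begin".
- **Comparison:** "The pre-and post-intervention scores, across each condition, for each subject", and also "for subjects undergoing the same condition, will be compared, to show the effect size, with 95% Confidence Interval".

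The paragraph names no analysis population. It does not say whether a condition means the one assigned or the one received, and it has no rule for switching, dropout or a missing post score. Nor does it say that anyone is to be left out. The number of arms, the allocation ratio and the choice between parallel and crossover design are not stated.

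**The concern.** Two phrases attract attention when read together. To undergo a condition describes, literally, what happened to a subject and not what was allocated. Counting 30 subjects by completed data collection suggests that those without a post score do not count. On that reading, a subject who was discharged early would vanish from the pre-post comparison, and a subject who received the other condition would be counted where they ended up.

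Either rule would matter in a randomised trial. Patients who leave neurorehabilitation early, or who end up with a different therapy, may well differ in prognosis from those who stay. Conditioning on completion or on treatment received lets that selection back in, and the confidence interval would not show it. A feasibility trial also has particular reason to account for everyone randomised, because retention is a natural feasibility result.

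**Working it through.** **1. What the wording commits the analyst to.**

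- *Grouping.* The comparison sentence never contrasts assigned with received treatment, and the section mentions neither switching nor non-adherence. With no such contrast, subjects undergoing the same condition are most naturally the subjects in the same arm.
- *Completion.* The sentence about 30 subjects ends with analysis beginning, so it is a trigger. Completing data collection also differs from completing the intervention: a subject who missed sessions but was assessed afterwards has complete data.
- *Design.* The phrase "The pre-and post-intervention scores, across each condition, for each subject" could also mean that each subject receives several conditions. Undergoing a condition would then be the natural verb, and allocation would be to a sequence.

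So no stated rule is wrong. The plan is silent.

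**2. How large the effect of that silence could be.** The documents give no dropout rate, switching rate, SD or allocation ratio, so there is no figure of theirs to reproduce. All inputs below are assumptions: two parallel arms of 15, SD of 1, no true effect.

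*Completer analysis.* Let d be the dropout fraction in one arm only, and g the shortfall in mean change of dropouts against completers, in SD. Bias = d × g.

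| d | g = 0 | g = 0.5 | g = 1.0 |
|---|---|---|---|
| 10% | 0 | 0.05 | 0.10 |
| 20% | 0 | 0.10 | 0.20 |
| 30% | 0 | 0.15 | 0.30 |

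With dropout in both arms the between-arm bias is d₁g₁ − d₂g₂, which is zero when rates and gaps are equal.

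*As-treated analysis, 2 of 15 controls receiving music therapy.* Suppose these 2 would do g SD better than the other 13. With the control-arm mean set to 0, the 2 have mean (13/15)g and the 13 have mean −(2/15)g. The as-treated difference is 2 × (13/15)g / 17 + (2/15)g = 0.102g + 0.133g = 0.235g. That is 0.12 SD at g = 0.5, 0.24 SD at g = 1.0, and 0 at g = 0.

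*As-treated analysis, share s of the music arm moving to control.* If switchers do g SD worse than stayers, the difference is gs + gs(1 − s)/(1 + s) = 2gs/(1 + s). At s = 10% this is 0.09 and 0.18 SD for g = 0.5 and 1.0. At s = 20% it is 0.17 and 0.33 SD. At g = 0 it is zero.

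*Precision.* The 95% half-width for a between-arm difference with 15 per arm is t(0.975, 28) × √(2/15) = 2.048 × 0.365 = 0.75 SD.

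**3. What the obvious remedies would gain.**

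*A likelihood-based longitudinal model.* There is one pre and one post score. A subject with only a pre score carries no direct information on the post mean. A constrained longitudinal model therefore gives nearly the same estimate as a baseline-adjusted comparison of those with post scores. Both rely on missingness being at random given baseline and arm. If dropouts would do worse for reasons the baseline does not capture, the bias tabulated above stays.

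*Counting the 30 as randomised.* At 20% loss, 30 × 0.8 = 24 have post scores, or 12 per arm. The half-width becomes t(0.975, 22) × √(2/12) = 2.074 × 0.408 = 0.85 SD, against 0.75 SD with 30 complete. Keeping 30 with complete data means randomising 30/0.8 = 37.5, so 38. The 8 without complete data can be reported under either definition.

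**The case for a change.** The strongest case for a change is that the plan can be followed to the letter in two ways, and the choice could be made after seeing the data. Nothing in the section commits to analysis as randomised, and a pre-post comparison drops subjects without a post score by default. The stated output is "to show the effect size, with 95% Confidence Interval", which readers would take as a randomised estimate. Bias of 0.1 to 0.3 SD would not show in that interval, and one sentence would close the gap at almost no cost.

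Part of this stands. The analysis set and the handling of missing scores are undefined, and an as-treated or complete-case analysis is not ruled out. If many subjects left one arm for reasons tied to outcome, the estimate would suffer.

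It does not turn the silence into an error. Each bias figure needs dropout or switching that is related to outcome and unbalanced between arms, and the documents give no rate for either. Nothing in the text suggests that controls are likely to receive music therapy, and nothing says that attrition will go unreported. The section also states no explicit between-arm contrast. That is a separate matter, but it means the paragraph cannot be said to break a comparison that it does not yet spell out.

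**Conclusion.** The concern does not hold as a fault in the plan. The text states neither an as-treated rule nor a completer rule; it leaves a gap that a competent analyst of a randomised trial fills by analysing subjects in their allocated arm (or by sequence and period, if each subject receives several conditions) and accounting for losses.

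The possible bias runs from 0 to 0.30 SD for one-arm dropout of up to 30%, and from 0 to 0.33 SD for switching of up to 20%, with prognostic gaps of up to 1 SD. These ranges rest on assumed rates and gaps, on two arms of 15, and on no true effect. They lie well inside the 0.75 SD half-width of an estimate that the plan itself calls exploratory. The wider interval does not excuse bias, but it does limit what anyone can conclude from this trial in either direction.

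The heavier remedies bring no clear gain. A longitudinal model with only two time points barely moves the estimate and leaves not-at-random dropout untouched. Counting the 30 as randomised would widen the interval from about 0.75 to 0.85 SD at 20% loss.
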